8.0 Reportable Events

- 8.1 Any adverse events or unanticipated problems involving risk to participants will be reported to the Indiana University Human Research Protection Program (HRPP) at [contact] or via email at [contact].
- 8.2 An adverse event (AE) for this study would be a side effect caused by the coconut oil used in the study. A serious adverse event (SAE) would be an anaphylactic reaction to the coconut oil used in the study. Collection of AEs and SAEs will begin at the start of interventions.

9.0 Data Safety Monitoring

- 9.1 Images obtained for the study will be saved in the standard way, using the Viewoint software.
- 9.2 Patient information will be entered into a secure RedCap: Name, MRN, BMI
- 9.3 Patient acceptability surveys will be entered directly into RedCap using an Ipad and dual-factor authentication.

10.0 Study Withdrawal/Discontinuation

- 10.1 At any time during the study, the participant can decide to withdraw themselves from the study at which point they will receive the ultrasound for which they were scheduled without the use of coconut oil as the ultrasound coupling media. Withdrawing from the study will not alter the care the patient receives.

11.0 Statistical Consideration

Study Design

There are 3 views for a given ultrasound, 2 raters will rate each image on 4 different factors, and each person will receive ultrasound using both types of medium (Coconut oil vs Commercial gel). Only image raters will be blinded to the medium used. Patients will be provided the two mediums in a different order (although the specific images will be in the same order). Quality will be estimated by two raters. Patient satisfaction with both mediums will be asked at the end of the ultrasound session and will ask patients how satisfied they were with each specific medium (Coconut oil vs Commercial gel) since they aren't blinded to type.

The study statistician will create a randomization list (A vs B) as to which medium each woman will receive first.

4 factors: Quality (Equivalence outcome), Resolution, Detail, Specific anatomic view (Based on a given image). All factors other than quality will be analyzed with a standard superiority hypothesis.

The primary hypothesis is that image quality (overall) will be equivalent between the two types of ultrasound medium. This will be tested using the within-patient contrast obtained from a linear mixed model.

Report Definitions

N is the number of items sampled from the population. Effect Size: $d = (\mu_1 - \mu_2) / \sigma$ is the effect size. Cohen recommended Low = 0.2, Medium = 0.5, and High = 0.8. σ is the assumed population standard deviation of the paired differences. Alpha is the probability of rejecting a true null hypothesis.

Our primary hypothesis for equivalence:

$$H_0: \delta \leq -10 \text{ or } \delta \geq 10 \text{ vs. } H_1: -10 < \delta < 10$$

With $N = 40$, an equivalence test of the mean difference in image quality (measured on 0 to 100 scale) from a paired design using two one-sided t-tests (which should provide similar power to the contrast from our model), achieves 83% power at .05 significance level when the actual paired difference is 5 and the estimated standard deviation of paired differences is 12 when equivalence limits are -10 and 10. For the continuous outcome of patient satisfaction, we will have 80% power to detect an $ES = 0.45$ with type I error set at .05 based on a paired t-test which provides similar power to the contrast from our model.

Statistical analysis

Descriptive statistics of image outcomes of quality, resolution, and detail will be summarized overall and separately by medium. For the specific anatomic view, this will be estimated separately for each view by medium. For the primary outcome, a linear mixed model will be fit to quality, including effects for view and medium (Coconut oil vs Commercial gel and a random rater effect. To test the hypothesis, the within-person mean difference in image quality for Commercial gel vs Coconut oil will be estimated along with associated **90%** confidence interval. If the confidence interval is inside the equivalence region of [-10, 10], we will reject the null hypothesis and conclude Coconut oil is equivalent to Commercial gel with regard to quality.

For all other image outcomes, a similar model will be fit except the mean difference in the outcome between mediums and associated **95%** confidence interval will be reported as we do not a priori know which medium will be better. Therefore, we report standard superiority hypothesis with type I error set at 0.05. For the outcome of the specific anatomic view, the model will only be fit for that specific image, thus the model will not contain the effect of view. All models will be examined for fit.

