5.0 Study Design

6.0 Enrollment/Randomization

- 6.1 Patients assigned to have their anatomy or growth ultrasound at the Maternal Fetal Medicine clinic in the Riley Outpatient Center will be approached to participate after the patient is roomed in the ultrasound suite and while they are waiting for the ultrasound technician to begin the scan.
- 6.2 The patient will be randomized to either starting the exam by first obtaining the study images with coconut oil and then proceeding with the standard ultrasound using commercial ultrasound gel or starting with the scheduled ultrasound using the commercial ultrasound gel and ending by obtaining the study images using coconut oil.
- 6.3 The same ultrasound machine will be used to obtain all images in this study. This means that only patients assigned to have their imaging in the ultrasound suite with the “study ultrasound machine” will be included in the study.

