7.0 Study Procedures

- 7.1 Recruitment and consent will take place in the ultrasound suite after the patient's vitals are collected and while they are waiting for the ultrasound technician to begin the ultrasound scan.
- 7.2 After the patient is consented and all questions are answered, the patient's information will be entered into a RedCap and they will be randomized to either starting the scan by first obtaining the required study images with coconut oil and then proceeding to the standard ultrasound using commercial ultrasound gel (Arm 1) or to starting with the scheduled ultrasound using the commercial ultrasound gel and ending by obtaining the required study images using coconut oil (Arm 2).

- 7.3 Whether assigned to Arm 1 or Arm 2, prior to the collection of the study images using coconut oil, the participant will be handed a small plastic cup with a pre-measured amount of coconut oil and they will be asked to warm it in their hand for at least 2 minutes. They will then apply the coconut oil to their own abdomen with their hands prior to the ultrasound technician obtaining the required images.
- 7.4 The ultrasound technician will collect 3 extra images for study purposes only using the coconut oil. This will only require 5-10 extra minutes of your time.
- 7.5 The ultrasound technician will drag the 3 fetal biometry images obtained with coconut oil and the 3 fetal biometry images obtained with commercial gel to the bottom of the set of images obtained throughout the study. They will label the images according to their randomization. For example, if randomized to coconut oil first followed by commercial gel, the coconut oil images will be labeled 1 and the commercial gel images labeled as 2. The images will be paired next to their counterpart.
- 7.6 While the images are being labeled and sorted, the patient will quickly fill out the short Patient Acceptability Survey.
- 7.7 The patient will be thanked for their participation and continue with the scheduled visit. A towel will be provided to clean off ultrasound gel or coconut oil as needed.

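### Order of medium is randomised and recorded but listed in no image model: a modest, nearly free gain in precision and balance is forgone, while the paired contrast stays valid on average

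*Combined protocol and SAP*

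**What the plan says.** Each woman is scanned with both media, and the order is assigned at random: "The study statistician will create a randomization list (A vs B) as to which medium each woman will receive first" (Section 11.0). In one arm the sequence is "first obtaining the required study images with coconut oil and then proceeding to the standard ultrasound using commercial ultrasound gel (Arm 1", as step 7.2 puts it. In the other it is "starting with the scheduled ultrasound using the commercial ultrasound gel and ending by obtaining the study images using coconut oil" (Section 6.2). Step 7.5 has the technician carry the order onto the images: "They will label the images according to their randomization". The first medium is marked 1 and the second 2. Neither the allocation ratio nor any blocking of the list is stated.

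For the primary hypothesis, Section 11.0 says "This will be tested using the within-patient contrast obtained from a linear mixed model". Under its statistical analysis heading, the model for quality is described as "including effects for view and medium (Coconut oil vs Commercial gel and a random rater effect". The other image outcomes get a similar model, and the model for the specific anatomic view drops the view effect. No order term is listed for any of them.

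A second random element sits elsewhere. Section 3.1 shows the paired images to the blinded reader in random order. That concerns display, not acquisition.

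**The concern.** The coconut oil images are taken before or after the scheduled scan, and the gel images during it. Fetal position, time on the table and the technician's familiarity with the patient could all differ between first and second acquisition. An order effect is therefore plausible, though the documents neither report nor assume one.

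If there is one and the analysis ignores it, two things follow. The order variation stays in the error of the paired differences, which costs precision. And if the two order groups are uneven in the analysed data, part of the order effect passes into the medium estimate, moving it toward or away from the ±10 margin. The information needed to deal with both is already recorded.

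**Working it through.** **Inputs from Section 11.0.** N = 40; equivalence limits -10 and 10; two one-sided tests at 0.05 (90% confidence interval); true difference 5 for power; SD 12, defined as the "assumed population standard deviation of the paired differences". For false equivalence the true difference is set at the limit, 10.

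**Assumed.** An order effect π (first minus second acquisition, 0-100 scale) of 0 to 8 points, additive and the same size for both media. This is a simplification, because the point in the scheduled scan at which gel images are taken is not stated.

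**Step 1: the plan's own figure.** SE = 12/√40 = 1.897. The normal approximation is 5/1.897 - 1.645 = 0.99, or 83.9% power. Exact integration with 39 df gives 82.7%. The stated 83% reproduces.

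**Step 2: model.** For each woman, d = δ + π (oil first) or δ - π (gel first), plus error with SD s. Since 12 is the total SD, s = √(144 - π²): 11.62, 10.91 and 8.94 for π = 3, 5 and 8. The paired test without order (N-1 df) was compared with the same test adjusted for order (N-2 df), by simulation with 100,000 trials per case for the main effects and splits.

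**Step 3: power at a true difference of 5, simple randomisation.**

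| π | Without term | With term | Change |
|---|---|---|---|
| 0 | 82.5% | 81.5% | about -1 |
| 2 | 82.7% | 82.7% | 0 |
| 3 | 83% | 84% | +1 |
| 5 | 83% | 88% | +5 |
| 8 | 83% | 96% | +13 |

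At a fixed 20/20 split, power goes from 84% to 85%, from 85% to about 88% and from 89% to 97% for π = 3, 5 and 8. With π = 0 nothing is lost.

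**Step 4: false equivalence without the term (true difference 10).** Under simple randomisation it is 4.9-5.0%. At 20/20 it is 4.4%, 3.5% and 1.4% for π = 3, 5 and 8. The test is conservative there because the order variation inflates the estimated standard error but not the actual error of the mean.

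**Step 5: uneven order groups.** The estimate shifts by π × (n1 - n2)/(n1 + n2). For π = 5:

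| Split | Shift | False equivalence without term, by direction | With term |
|---|---|---|---|
| 24/16 | 5 × 8/40 = 1.0 | 11% or 1% | 5% |
| 20/16 | 5 × 4/36 = 0.56 | 6.6% or 1.7% | 5% |
| 20/18 | 5 × 2/38 = 0.26 | 4.9% or 2.5% | 5% |

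If the list is unrestricted, a split of 24/16 or worse has probability 27% (binomial, 40 draws at 0.5).

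**Step 6: dependence on the patient terms.** An image-level simulation used 480 ratings (40 women × 2 media × 3 views × 2 raters) at 20/20, with assumed patient SD 5-15, image SD 8-10, rating SD 8-10 and a total paired SD of 12. With only the listed terms (view, medium, rater), adding order changed power by under 1 point at π = 5. With patient and patient-by-medium effects, it raised power from 84-85% to 88-89%. In both, the term removed the 1.0-point shift at 24/16.

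**The case against.** The strongest reply is that randomising the order already protects the test, and that the benefit rests on an order effect nobody has shown. Much of this stands. On average over allocations the error rate is nominal. Under simple randomisation the term gains nothing below about 2 points and costs about 1 point of power at zero. The larger gains need effects of 5 to 8 points, half to four-fifths of the margin, within one visit on one machine. The 11% figure needs a 5-point effect, a 24/16 split and the unfavourable direction together, and whether the list is restricted is unknown.

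It can also be said that the model description is evidently incomplete: it lists no patient term although the contrast is meant to be within patient. The supportable statement is therefore that no order term is listed, not that none would be fitted.

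What survives is that protection on average does not help the one trial that is run if its split is uneven, and that the remedy uses a factor already randomised and recorded.

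A reader might infer four stronger things, which the documents do not support:

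- **That the equivalence test is invalid without the term.** Steps 3 to 5 show otherwise for the paired contrast.
- **That the stated power is overstated.** That holds only if 12 excludes order variation (power without the term would then be 81%, 77-79% and 70-73% at 3, 5 and 8 points). Section 11.0 defines 12 as the SD of the paired differences, which is the total.
- **That withdrawals will unbalance the comparison.** Section 10.0 does allow it: "At any time during the study, the participant can decide to withdraw themselves from the study". But the loss of a few women does little, as the 20/18 row shows.
- **That any error inflation in the model as listed comes from omitting order.** It comes from the missing patient terms and arises with no order effect at all. That is a separate issue.

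**Conclusion.** The point holds as a minor improvement. Acquisition order is what each woman is randomised to and is recorded, yet it is listed in no image model. The within-patient contrast remains valid on average and the 83% stands. The plan forgoes between roughly -1 and +13 points of power over an assumed order effect of 0 to 8 points, and protection against a shift when the order groups are clearly uneven.

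These figures rest on an additive order effect, a total paired SD of 12 and N = 40. The power gain further requires that the model really makes the contrast within patient. The term adjusts only an average first-versus-second difference. It would not correct differential carryover, such as residue of one medium affecting the second set of images differently from the other.

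**What to change.** In the statistical analysis part of Section 11.0, add a fixed effect for acquisition order (first versus second medium, the 1/2 label of step 7.5) to the primary and other image models. State that the medium contrast is fitted within patient, as the primary hypothesis requires. Either include random effects for patient and patient-by-medium, or analyse each woman's mean oil-gel difference with order as a covariate coded +1/-1, so that the intercept weights the two orders equally. The term must be first versus second acquisition: a between-patient effect for sequence alone would leave the within-patient contrast unchanged. Make the change before the ratings are analysed by medium, so that it is not a post hoc choice.

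The cost is one degree of freedom and no new data. If there is no order effect, the power loss is nil at 20/20 and about 1 point under simple randomisation.

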3.0 Outcome Measures/Endpoints

3.1 Image Quality

- Paired images will be displayed side by side in random order and each of the following parameters will be assessed using a 10 cm visual analog scale by a blinded reader:
 - Resolution – sharpness/crispness of image, lack of haziness
 - Image detail – clarity of organ outlines and ease with which boundaries of structures are seen
 - Total image quality – contrast of solid and fluid-filled structures and absence of noise
 - Clarity/definition:
 - BPD/HC – thalami and CSP
 - Abdominal circumference – umbilical vein, portal sinus
 - FL - femur bow definition

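### In an equivalence study, do resolution, detail and anatomic clarity also need an equivalence margin?

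*Combined protocol and SAP*

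**What the plan says.** Section 3.1 of the combined protocol and SAP lists resolution, image detail, total image quality and view-specific clarity together, and "each of the following parameters will be assessed using a 10 cm visual analog scale by a blinded reader". Section 11.0 then separates them: "4 factors: Quality (Equivalence outcome), Resolution, Detail, Specific anatomic view (Based on a given image"). The primary hypothesis concerns one of the four: "The primary hypothesis is that image quality (overall) will be equivalent between the two types of ultrasound medium". It carries limits of -10 and 10 on a 0 to 100 scale and a 90% confidence interval rule. If the interval lies inside the limits, the investigators will "conclude Coconut oil is equivalent to Commercial gel with regard to quality".

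For the others the rule is "All factors other than quality will be analyzed with a standard superiority hypothesis". The statistical analysis text of section 11.0 specifies a similar mixed model, the mean difference between media and a 95% confidence interval. The reason given is "as we do not a priori know which medium will be better", and it goes on: "we report standard superiority hypothesis with type I error set at 0.05". No margin, SD or power is stated for these factors.

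**The concern.** Section 1.0 presents the trial as an equivalence study of coconut oil as a substitute for gel, and all four factors are scored on the same scale. A reader may therefore expect the same question of each: is oil close enough? For three of the four, the plan fixes in advance only how to declare a difference.

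The stated reason seems to make this worse. Not knowing which medium is better justifies a two-sided test. It does not favour a difference test over an equivalence test, since limits of -10 and 10 are themselves symmetric in direction.

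Two harms could follow. The same numerical difference might be reported as equivalent for quality and as significantly different for resolution. Or a non-significant result on a noisy factor might be taken as reassurance. A margin chosen after the results were seen would settle neither credibly.

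**Working it through.** **Inputs.** From section 11.0, for quality only: N = 40 pairs, limits ±10, α = 0.05 per one-sided test, and power computed "when the actual paired difference is 5 and the estimated standard deviation of paired differences is 12". Using these limits or any SD for another factor is an assumption. The paired t-test stands in for the mixed-model contrast, as it does in the plan's own power statement. With 39 degrees of freedom, t(0.975) = 2.0227 and t(0.95) = 1.6849.

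**Step 1: the plan's own figure.** Exact power of two one-sided paired t-tests at difference 5, SD 12, limits ±10 and N = 40 is 82.7%, against the stated 83%. It reproduces.

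**Step 2: rules for another factor.** Let m be the observed mean difference and s the observed SD of the paired differences.

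- Significant: |m| > 2.0227·s/√40.
- Within ±10 by the 90% interval: |m| + 1.6849·s/√40 < 10.
- Within ±10 by the planned 95% interval: |m| + 2.0227·s/√40 < 10.

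At s = 12:

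- smallest significant difference: 2.0227 × 12/√40 = 3.84
- largest difference within ±10 by the 90% interval: 10 − 1.6849 × 12/√40 = 6.80
- largest difference within ±10 by the 95% interval: 10 − 3.84 = 6.16

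Observed differences from 3.84 to 6.80 are thus both significant and within the limits.

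**Step 3: how often this happens** (numerical integration, normal mean, chi-square variance).

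| True SD | True difference | Significant | Significant and within (90% CI) | Neither significant nor within |
|---|---|---|---|---|
| 12 | 2 | 17.7% | 17.1% | about 0 |
| 12 | 3 | 33.8% | 31.4% | about 0 |
| 12 | 5 | 72.9% | 55.7% | about 0.001% |
| 15 | 5 | 53.8% | 21.2% | 0.9% |
| 17 | 5 | 44.2% | 7.3% | 5.8% |
| 20 | 5 | 33.8% | 0.8% | 20.7% |

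At SD 12 and difference 5, the planned 95% interval by itself lies inside ±10 in 45.8 of the 55.7 percentage points. No additional interval is needed in those trials.

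**Step 4: when could a non-significant result mislead?** A result can be neither significant nor within ±10 only if 2.0227·s/√40 + 1.6849·s/√40 > 10, that is s > 10·√40/3.7076 = 17.06. The only SD in the documents is 12.

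**Step 5: do the two headlines conflict?** No. Significant means the difference is distinguishable from zero; within the margin means it is smaller than 10. A true difference of 5 satisfies both. Quality itself would show the same pattern under the plan's own assumptions: an effect of 5 that passes the equivalence test and also has a 95% interval excluding zero in 72.9% of trials.

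**Step 6: what the text permits.** The equivalence conclusion in section 11.0 is confined to quality. For the other factors the plan reports an estimate and interval, and no sentence turns a non-significant result into a claim of equivalence.

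**The case for a change.** The strongest case for the concern is that the stated reason does not support the choice, and that part stands. Unknown direction supports a two-sided 95% interval, but the step from there to a superiority hypothesis does not follow. This is a fault of rationale. The analysis it introduces is still valid.

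It is also true that an interval without a margin fixed beforehand does not say how close is close enough, and that section 3.1, which the table of contents files under primary outcome measures, lists these factors beside total quality. The documents never label them secondary. Section 11.0 does settle which factor carries the primary hypothesis, however, and a trial with one primary equivalence claim need not set a margin for every supporting measure. Testing the components for differences can reveal a deficit that the overall score hides.

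Adding margins has its own price: up to five further equivalence statements (resolution, detail, three views) without multiplicity control, on limits the documents justify for none of them. If single-view scores are noisier, equivalence power at difference 5 falls from 83% at SD 12 to 67% at SD 15, 46% at SD 20 and 33% at SD 25. Statisticians could reasonably choose either way.

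**Conclusion.** The concern does not hold. The plan deliberately makes one equivalence claim and gives the remaining image factors a fully specified two-sided difference analysis; carried out as written, it leads to no wrong conclusion. The primary test, its 83% power and the sample size are untouched. The apparent contradiction, about 56% of trials at difference 5 and SD 12, consists of two compatible statements about the same estimate, and the reported 95% interval lets any reader compare that estimate with any margin. False reassurance is about 0.001% or less at SD 12 for true differences from 0 to 5, and can arise only with an observed SD above 17.06.

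These figures assume that quality's limits and SD apply to the other factors, which the documents do not say. At SD 20 the chance of a result neither significant nor within ±10 would be 10% to 21% for true differences from 0 to 5. Even then an error would require reading non-significance as equivalence, which the plan does not propose. What remains is a weakly argued reason for a legitimate choice.

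### The primary mixed model names no patient-level term, so the 90% interval that decides equivalence does not reflect the pairing on which the 5% error and 83% power rest

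*Combined protocol and SAP*

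**What the plan says.** All of this is in Section 11.0 of the combined protocol and SAP.

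- **Intended contrast.** For the primary hypothesis the design text says: "This will be tested using the within-patient contrast obtained from a linear mixed model". The analysis text says that "the within-person mean difference in image quality for Commercial gel vs Coconut oil will be estimated".
- **Model.** The terms given are "including effects for view and medium (Coconut oil vs Commercial gel and a random rater effect". Rater is the only random effect named.
- **Decision rule.** "If the confidence interval is inside the equivalence region of [-10, 10], we will reject the null hypothesis". The interval is a 90% interval, and this is the only rule for the primary hypothesis.
- **Sample size.** 83% power with 40 patients at a true difference of 5, obtained "using two one-sided t-tests (which should provide similar power to the contrast from our model"), where "the estimated standard deviation of paired differences is 12 when equivalence limits are -10 and 10".
- **Data structure.** "There are 3 views for a given ultrasound, 2 raters will rate each image on 4 different factors", and every patient is scanned with both media.
- **Other image outcomes.** They use a model of the same kind with a 95% interval. For the anatomic-view ratings, "the model will only be fit for that specific image, thus the model will not contain the effect of view".

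No patient random effect, patient-by-medium effect, repeated-measures covariance or robust standard error is named anywhere in the document.

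**The concern.** A model whose only random effect is rater treats two ratings from the same patient as no more alike than ratings from two different patients. This can distort the standard error in either direction.

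- Differences between patients in general image quality cancel in a paired comparison. In the listed model they stay in the residual and make the interval too wide.
- Variation between patients in the oil-gel difference itself does not cancel. A paired analysis averages it over 40 patients. The listed model treats it as independent noise over 240 ratings per medium, which makes the interval too narrow.

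The primary conclusion depends only on whether the interval lies within ±10, so its width matters as much as its centre. If it is too narrow, equivalence is declared too often at the margin. If it is too wide, the trial has less power than stated. The claim that the paired test has power similar to the model's contrast has no support for the model as listed.

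**Working it through.** **1. The plan's own figure.** Inputs: n = 40, SD of paired differences 12, true difference 5, margins ±10, 5% per side. The standard error is 12/√40 = 1.897 on 39 df. Exact power of the two one-sided paired t-tests is 82.7%, which matches the stated 83%. Error at a true difference of 10 is 5.0%, and the 90% half-width is about 3.20. The sample-size statement is therefore right for a paired test.

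**2. Standard error of the listed model.** Ratings per patient: 3 views × 2 raters × 2 media = 12. In total: 40 × 12 = 480, or 240 per medium. Let T be the SD of a single rating after view, medium and rater are removed.

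- SE = T × √(1/240 + 1/240) = 2T/√480
- df = 480 − 1 (mean) − 1 (medium) − 2 (view) − 1 (rater) = 475

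**3. Where the two agree.** Setting 2T/√480 = 1.897 gives T = 1.897 × √480/2 = 20.8. The document gives no rating SD, so nothing shows that T is near this value.

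**4. Consequence by rating SD.** T is assumed. The true standard error is held at 1.897 and the estimate is taken as Normal. With half-width h = t(0.95; 475) × SE, false equivalence at a true difference of 10 is about Φ(−h/1.897), and power at 5 is about Φ((5 − h)/1.897). For T = 12: SE = 24/√480 = 1.10, h = 1.81, error = Φ(−0.95) = 17%, power = Φ(1.68) = 95%.

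| Assumed T | SE | False equivalence at 10 | Power at 5 |
|---|---|---|---|
| 12 | 1.10 | 17% | 95% |
| 15 | 1.37 | 12% | 93% |
| 18 | 1.64 | 8% | 89% |
| 20.8 | 1.90 | 5% | 84% |
| 25 | 2.28 | 2.4% | 74% |
| 30 | 2.74 | 0.9% | 60% |

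**5. Simulation by source of variance.** The balanced 40 × 2 × 3 × 2 design was simulated 20,000 times per setting. The paired-difference variance was fixed at 144 = 2 × (patient-by-medium variance) + 2 × (residual variance)/6. The share of the 144 due to patient-by-medium variation and the between-patient SD are assumptions. Each cell gives error at 10 / power at 5 for the listed model, in %.

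| Patient-by-medium share | Between-patient SD 0 | SD 10 | SD 15 | SD 20 |
|---|---|---|---|---|
| 0% | 5.1 / 83.8 | 3.5 / 78.8 | 2.3 / 72.7 | 1.1 / 63.7 |
| 50% | 10.5 / 91.8 | 7.3 / 87.6 | 4.5 / 82.2 | 2.3 / 72.9 |
| 90% | 20.4 / 96.6 | 12.9 / 93.3 | 8.0 / 88.2 | 4.1 / 80.5 |

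In the same data, a t-interval on patient-level paired differences gave 4.9–5.2% error and 82.2–83.1% power in all twelve settings. The point estimate of the listed model equalled the mean paired difference to rounding error.

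**6. A patient intercept alone.** Adding only a patient intercept (475 − 39 = 436 residual df) gave error of about 5% at a 0% share, 11–12% at 50% and 24% at 90%. It is correctly sized only if the oil-gel difference does not vary between patients and there is no image-level variance shared by the two raters.

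**7. Other image outcomes.** For resolution and detail, if the paired-difference SD is also assumed to be 12, the two-sided error of the 95% interval is about 26 / 16 / 4.9 / 1.8 / 0.5% at T = 12 / 15 / 20.8 / 25 / 30. A single-view model has 40 × 2 × 2 = 160 ratings and SE = 2T/√160 = T/√40. Its interval is correctly sized only if T equals the paired-difference SD for that view.

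**The case against.** The best defence is that the intent is plain. Section 11.0 twice describes a within-patient or within-person contrast and sizes it as a paired design. The list of terms is introduced by a word that need not mean it is complete, and its bracket is never closed, so words may have dropped out. A competent analyst would add a patient effect. With complete data the estimate does not change, and the sample-size calculation stands.

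Much of this is fair. A patient effect was probably intended. But no part of the document names one, and the stated intent does not say which patient structure to fit. Step 6 shows that the most obvious choice, a patient intercept, can itself give error well above 5%. The promise to examine models for fit names no term, and choosing the covariance after seeing the data is not prespecification.

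Three cautions about the size also stand.

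- The direction is unknown, and a conservative interval is as open as a liberal one. Inflation needs a varying oil-gel difference or image-level variance. With neither, the listed model is correctly sized or conservative.
- The highest error figures need an oil-gel difference that varies between patients with an SD of about 11, larger than the margin itself.
- The document does not define the unit of its SD of 12. The figures here take it as the SD of patient differences averaged over six ratings per medium.

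**Conclusion.** The concern holds and should be settled before analysis. As written, the primary model gives the deciding 90% interval a standard error of 2T/√480 on about 475 df, which has no necessary link to the 1.90 on 39 df behind the power statement. Over the settings examined, error runs from about 1% to 20% instead of 5%, and power from about 60% to 97% instead of 83%. Neither figure can be relied on for the listed model.

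These ranges assume 40 complete patients, Normal ratings, the model fitted exactly as listed, and 12 as the SD of patient-level mean differences. They illustrate what could happen and do not predict what will. The mismatch between the two standard error formulas does not depend on the assumed rating SDs. With complete data only the standard error, df and interval are affected. If images are missing, the listed model's estimate would also cease to be purely within-patient.

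**What to change.** State the patient-level structure in the Statistical analysis part of Section 11.0. Either of these would do:

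- **Paired means.** Average each patient's six quality ratings per medium, take the difference, and report the 90% paired t-interval (39 df with 40 complete pairs). This is the analysis that the 83% refers to. State how a missing image or rating is handled.
- **Mixed model.** Keep view, medium and random rater, and add random effects for patient and for patient-by-medium, with Kenward-Roger or Satterthwaite df.

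In complete balanced data the two agree when the patient-by-medium variance estimate is above zero. If that estimate falls to zero the mixed model can be conservative, and paired means avoid this.

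Use the matching structure for resolution and detail. For each single-view anatomic model this means two ratings per patient per medium and no view term.

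The cost is one or two sentences, with no new data or patients. The interval may turn out wider than the listed model would have given.
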